A randomized controlled trial to assess the performance and safety of a novel Ostomy Ring (Osto Ring™) to improve ileostomy and colostomy management
[name], [name] [name]

Background and Significance:

Ostomy surgery refers to a surgical procedure in which part of the intestine is removed and the intestinal contents are rerouted through the abdominal wall via a stoma (<http://www.niddk.nih.gov/health-information/health-topics/digestive-diseases/ostomy-surgery-bowel/Pages/ez.aspx>). This type of surgery results in the patients utilizing an external pouch, a plastic bag affixed around the stoma on the abdominal skin to collect the waste. Depending on the reason for the surgery, stomas may be temporary or permanent.

It was estimated in 2012 that there are 1 million people in the United States and Canada living with ostomies, with an additional 100,000 new ostomies created per year in the United States. (Mitchell KA, Rawl SM, Schmidt CM, et al. Demographic, clinical, and quality of life variables related to embarrassment in veterans living with an intestinal stoma. *J Wound Ostomy Continence Nurs.* 2007;34(5):524-532).

The quality of life for patients who undergo this type of surgery is significantly affected. It is an adjustment for a patient to psychologically understand that his or her body will no longer perform a bodily function “normally”. The patient needs to learn new skills such as how to correctly apply the pouching system, adjust wear time, and learn how and when to empty the pouch and remember to check the pouch seal to detect any signs of leakage. These new skills take time to learn and one of the greatest challenges is to find the best pouching system that can provide a consistent wear time to prevent leakage, embarrassment and peristomal skin issues.

A new device has been created with the aim of improving wear time and decreasing problems with leakage. The Osto Ring™ (GoDuRn LLC, [name]) is a novel and proprietary add-on modifier to the Hollister 2 piece New Image pouching system that creates a more secure seal between the patient’s peristomal skin and the skin barrier, and therefore reduces the risk of leakage.

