We hypothesize that the addition of the Osto-Ring™ will reduce leakage from the stoma appliance and may also increase the length of time needed between pouch changes. Currently, the mean ostomy pouch wear time in the United States is 5.2 days (Richbourg L, Fellows J, Arroyave WD. Ostomy pouch wear time in the United States. *J Wound Ostomy Continence Nurs.* 2008 Sep-Oct;35(5):504-8), and out-of-pocket costs can be as high as \$30 with each pouching system change which translates to a yearly cost of close to \$3000. Longer wear time would therefore translate into needing fewer ostomy bags and less money spent on ostomy supplies.

Overall Objective:

The primary objective of this pre-market study is to assess the safety and performance of the Osto Ring™ as it relates to the pouching system wear time and degree of leakage.

Protocol Version #1
Dated 4/22/19

Research Design:

Study population: 30 adult subjects who have had an ileostomy or colostomy for at least 6 months, who currently use the Hollister New Image 2 piece pouching system acting as their own controls, will use their standard 2 piece New Image Hollister pouching system without the Osto Ring™ for 28 days. On Day 29 subjects will be switched to the Osto-Ring regimen until day 56. Patients will be evaluated in person at Day 0 and approximately Days 28, 56, and 75 (within business days and scheduling convenience).

The Osto-Ring for this study is being supplied by GoDuRn, LCC, and provided to subjects free of charge.

During the standard of care visit to the health care provider, subjects will be evaluated to confirm that they meet the criteria for participating in this study.

Study Design:

Day 0-27

Visit One

- **Subject will wear their standard of care Hollister 2 piece New Image pouching system for 28 days.**
 - At the first visit they will remove their pouching system to allow the investigator to assess their skin (research staff will take photo) using the Ostomy Skin Tool Reference Guide [See appendix B]
 - They will be given and asked to fill out the Quality of Life Questionnaire [See appendix C]
 - They will be given Ostomy Evaluation Record [See appendix A] and asked to complete this at every pouching system change. (And take photos of the skin site and adhesive side of the ostomy flange.)

Day 28-55

Visit Two

- **Subjects will now wear their standard of care Hollister 2 piece New Image pouching system with the Osto-Ring for the next 28 days.**

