 - At the first visit they will remove their pouching system to allow the investigator to assess their skin using the Ostomy Skin Tool Reference Guide [see appendix B] (photo taken)
 - They will be fitted for the proper Osto-Ring size and given a belt.
 - They will be given and asked to fill out the Quality of Life Questionnaire [See appendix C]
 - They will be given 2 questionnaires and asked to complete them at every pouching system change. Subject will take photograph at each stoma change
 - Ostomy Evaluation Record [See appendix A]
 - Osto Ring Evaluation Record [See appendix D]

Day 56

Visit Three

Patients will decide if they want to continue using the Osto-Ring™ with their standard of care pouching system.

- Their pouching system will be removed and will have a skin assessment by the investigator using the Ostomy Skin Tool Reference Guide, Appendix B.

Protocol Version #1

Dated 4/22/19

- They will be asked how they are doing and to report any side effects they may have experienced even if they do not think it is related to the Osto-Ring™.
- They will be asked to complete :
 - The Ostomy Quality of Life Questionnaire

If they felt that the Osto Ring was helpful, subjects will be asked to extend the wear of their devices by 1-4 days per their experience (if possible). Photographs will be taken at each stoma change of the skin and the adhesive side of the flange.

Day 75

Visit Four

At this last visit, patients can decide to have their Osto Ring removed or continue using it if they like.

All four of the clinic visits are considered research-related, along with completion of questionnaires and peristomal skin assessment.

During this study, [name] and his research team will collect information about the patients for the purposes of this research. This includes their name, telephone number, medical record number, initials, date of birth, medical, surgical and medication history, date of study entry, dates of study procedures and results of tests and procedures done as part of the study.

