To calculate the study sample size, data from prior studies and expert opinion was used for power analysis since this device uses a novel approach to increase wear time. The mean wear time for ileostomy pouches in the United States is 5.01 +/- 2.25 days (Richbourg L, Fellows J, Arroyave WD. Ostomy pouch wear time in the United States. *J Wound Ostomy Continence Nurs.* 2008 Sep-Oct;35(5):504-8). An increase of wear time by 25% to 6.26 days is beneficial for patient care. We determined the effect size to be 0.56 assuming that the pool standard deviation is similar to the study cited above. Using a paired t-test with a significance level of 0.05 and power of 0.8, 27 patients are needed for this study.

All patients will be recruited from the NorthShore University HealthSystem IBD center and General Surgery Clinics. Evaluation and management for any stoma related questions, concerns or assessments may also be provided by our IBD center team. Results of the study will not be made available to the sponsor or anyone with a perceived or actual conflict of interest (eg actual/potential financial relationship) until the statistical analysis has been independently completed.

Inclusion Criteria:

Subjects interested in participating in the clinical investigation must comply with the following criteria:

1. Are at least 18 years of age and have full legal capacity
2. Have had an end or loop ileostomy or colostomy for at least 6 months.
3. Have used a Hollister 2 piece New Image pouching system for at least 8 weeks
4. Able to provide informed consent
5. Have a stoma with a diameter of 57mm or less

Protocol Version #1

Dated 4/22/19

6. Change their pouching system at least two times in seven days

Exclusion Criteria:

Subjects complying with the following criteria must be excluded from participation in the clinical investigation:

1. Unable to give informed consent.
2. Are pregnant or currently breastfeeding.
3. In the last 2 months has received or is currently receiving, chemotherapy or radiation therapy.
4. In the last month has received or is currently receiving systemic or local steroid treatment in the peristomal area.
5. Currently suffering from severe peristomal skin problems such as peristomal pyoderma, abscess.
6. Currently suffering from a peristomal hernia.
7. Known hypersensitivity toward any of the test product (Osto Ring™ is made of surgical grade stainless steel)
8. In the last 30 days has participated or is currently participating in a clinical study

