9. Assessed with an ostomy skin tool score of ≥ 3

Primary Outcomes:

Performance Efficacy:

To evaluate the Osto Ring™ for pouching system wear time, and degree of leakage in subjects when using the Osto Ring™ as compared to when not using the Osto-Ring™

- Integrity of the adhesive side of the flange (photos)
- Wear Time:
 - Total time pouching system worn will be calculated by the Ostomy Evaluation Record. This is defined as the difference between the dates and times the appliance is changed. (Appendix A)
- Leakage:
 - Degree of leakage at time of pouching system changes will be measured using line item from Ostomy Evaluation Record (Appendix A)

Secondary Outcomes:

1. The condition of the peristomal skin and stoma (Appendix B)
2. The number and frequency of adverse events
3. The subjects' quality of life using the Stoma Quality of Life (QoL) questionnaire (Appendix C)
4. Subject Ease of Use (ease of application, pain level with application, comfort, convenience of use) will be assessed using Likert scale: 1 = poor, 2 = satisfactory 3= very good, 4= excellent (Appendix D)

Analysis plan:

Protocol Version #1

Dated 4/22/19

All means and frequencies will be compared between the groups with the Osto Ring™ versus the group without it and will be controlled for the order in which a subject used the Osto Ring.

- Wear Time:
 - Mean days in between pouching system changes
- Leakage:
 - Frequency of any degree of leakage at pouching system changes
 - Frequency of much leakage at time of pouching system change
- Skin condition:
 - % of patients with moderate to severe skin conditions at time of each WOC nurse or physician study visit
 - Mean % of time with moderate to severe skin conditions throughout the 4 week interval at every WOC nurse or physician study visit
- Quality of Life:
 - Mean quality of life scores
- Time per Ostomy Care Session
 - Mean minutes spent during ostomy care session
- Ease of Use
- Mean % of time ease of use reported as very good or excellent by subject , Satisfaction and Confidence
 - Mean satisfaction and confidence scores
- Device Recommendation
 - % of subjects reporting they strongly agree to recommend the device to others

We will compare the baseline characteristics of the two groups. Continuous variables will be compared with the paired *t* test, and categorical variables were compared with the Fisher exact test. Each item on the ostomy evaluation record form will be individually reported.

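### Wear time counts changes made for any reason and leakage is counted per change, so these two summaries alone cannot separate a longer changing habit from a better seal; combining items already on Appendix A largely can.

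*Combined protocol and SAP*

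**What the plan says.** **Outcome.** Under Primary Outcomes, wear time comes from the Ostomy Evaluation Record: "This is defined as the difference between the dates and times the appliance is changed". The Analysis plan summarises it as mean days between changes, with no distinction by cause. Leakage is the frequency of any leakage, and of much leakage, at changes. Integrity of the adhesive side of the flange, from photos, is also listed as primary. Each item of the record is to be reported individually.

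**Design.** Research Design fixes the order: "On Day 29 subjects will be switched to the Osto-Ring regimen until day 56". Neither 28-day period has a rule on when to change. Only after Day 56 is wear length addressed: "If they felt that the Osto Ring was helpful, subjects will be asked to extend the wear of their devices by 1-4 days".

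**Wear as partly a choice.** Background and Significance says patients must learn "how to correctly apply the pouching system, adjust wear time" and that a main challenge is to "find the best pouching system that can provide a consistent wear time to prevent leakage". The hypothesis is that the ring "may also increase the length of time needed between pouch changes".

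**Forms.** Appendix A, completed at every change, records days since the previous change, amount of leakage, and days in place before leakage was noted. It does not ask why the change was made. Appendix D item 6 asks only whether the pouching system was altered, and only in the ring period. The safety section obliges subjects to mention departures from their changing routine, but no form field or analysis uses this.

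**The concern.** A change can be forced by a leak, follow a routine, respond to skin or comfort, or happen because a clinic visit required removal. The claimed mechanism, a better seal, acts directly only on the first. In a fixed-order study without blinding, subjects may also stretch their routine while wearing a device meant to last longer.

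This works in two directions. Routine changes dilute a true seal benefit in mean wear time, and a longer routine raises wear time with no seal benefit. The leakage outcome does not settle it alone, because a longer interval gives each pouch more time to leak. A result of longer wear with no clear difference in leakage per change could then be habit alone, or habit plus a better seal. What is at stake is how a wear-time gain is attributed, not whether wear time may be measured.

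**Working it through.** **Inputs from the documents.** Mean 5.01 days, SD 2.25, target 6.26 and n = 27 (sample-size paragraph; "An increase of wear time by 25% to 6.26 days is beneficial for patient care"); 30 subjects and two 28-day periods (Research Design); longest average entry interval 7/2 = 3.5 days (Inclusion item 6: "Change their pouching system at least two times in seven days").

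**Assumptions.** p is the share of control-period changes forced by leakage; it is not in the documents, so a range is shown. The habit shift of 1 day is illustrative. It equals the smallest extension requested after Day 56, but that request does not govern Days 28-55.

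**1. The plan's own figure.** d = 1.25/2.25 = 0.556, rounded to 0.56. A two-sided paired t test at 0.05 has power 0.7998 with 27 subjects and 0.84 with 30. The stated 27 reproduces.

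**2. Per change against per day.** Leaks per day worn = leakage per change / mean wear. If leakage per change is unchanged while wear goes from 5.01 to 6.26 days, leaks per day fall by 1 - 5.01/6.26 = 20.0%. The planned leakage frequency shows no difference.

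**3. Closed forms.** Take a fixed routine T and a constant daily leak hazard h, with each leak forcing a change. Then p = 1 - exp(-hT) and mean wear = p/h.
- Habit only, T from 3.5 to 4.5: leakage per change p' = 1 - (1-p)^(4.5/3.5); wear ratio p'/p.
- Seal only, h halved: p' = 1 - sqrt(1-p); wear ratio 2/(1 + sqrt(1-p)).

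| p | Habit: wear | Habit: leakage per change | Seal: wear | Seal: leakage per change |
|---|---|---|---|---|
| 10% | +27% | 12.7% | +3% | 5.1% |
| 20% | +25% | 24.9% | +6% | 10.6% |
| 30% | +23% | 36.8% | +9% | 16.3% |
| 40% | +20% | 48.1% | +13% | 22.5% |

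In this model habit does not alter leaks per day, because h is unchanged.

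**4. Simulation.** 30 subjects, routine 2.5-3.5 days, jitter SD 0.5 day, between-period drift SD 0.5 day, gamma hazard with CV 0.7, visit-truncated intervals left out of mean wear and per-change leakage, paired t at 0.05. All inputs are assumed. Percentage of trials significant at p = 10, 20, 30, 40%:

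| Truth | Wear time | Leakage per change | Leaks per day | Interval at no-leak changes |
|---|---|---|---|---|
| Hazard halved, same routine | 8, 23, 47, 67 | 53, 82, 97, 100 | 54, 85, 98, 100 | about 3-7 |
| Routine +1 day, no seal effect | 100 throughout | 19, 27, 42, 48 (upward) | 4 throughout | 100 |
| Hazard x0.8, routine x1.25 | 100 throughout | 7, 4, 3, 6 | about 13-34 | not needed |

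A pure seal benefit usually shows in planned leakage unless p is low. The last two rows are hard to tell apart on wear time and leakage per change: both give a certain wear-time gain, and leakage per change is often not significant. The no-leak interval, computable from Appendix A as it stands, detects the habit shift. It still did so in 100% of habit trials, against 3-5% of seal-only trials, when half or all leaks were found only at removal.

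The 100% for wear time depends on the assumed drift SD. With the plan's SD of 2.25 and 30 subjects, a habit gain of 1 day is significant in 65% of trials and 0.5 day in 22%.

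**5. Days 56-75.** The plan does not say whether these records enter the comparison. Starting from 3.5 days with no ring effect, pooling an extension of e days gives a ring mean of 47/(28/3.5 + 19/(3.5+e)). For e = 1 this is 3.85 (+0.35 day, 10%); for e = 4 it is 4.46 (+0.96 day, 27%), just above the 25% target.

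**The case against.** The strongest reply is that the data already discriminate. Appendix A gives leak status, interval and days before leakage was noted; set against each other, these are a fair proxy for a leak-prompted change. Flange photos bear directly on the seal, and every Appendix A item is to be reported. This largely stands. A reader might infer that the trial cannot tell habit from seal at all, or that it depends on a reason box; the documents do not support either. What is missing is the combination: item-by-item reporting does not give leaks per day worn or wear time split by leak status.

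A second reply is that the interval between changes is the right measure for the aim of fewer pouches and lower cost, and that wearing longer because the seal is trusted may be part of the device effect. This also stands, so the inference that the primary outcome is invalid, or that the test or sample size must change, is not supported.

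Third, both compared periods are equally silent on when to change, and subjects have had the stoma for at least 6 months and this system for at least 8 weeks. That reduces the scope for drift but does not stop subjects stretching wear in the later ring period. A reader might conclude that a change rule must be imposed. The documents do not require one, and it is a trade-off: holding subjects to their routine limits the gain that can appear, and a set maximum caps the outcome and may alter usual care. It is left to the investigators.

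**Conclusion.** The point holds in a limited form. Mean wear time and leakage per change, taken alone, cannot separate a longer changing habit from a better seal. At the plan's target, unchanged leakage per change hides a 20% fall in leaks per day worn; that figure is arithmetic on the plan's numbers. Everything involving p, the habit shift, the hazard or the drift is assumption, so the real size is unknown.

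Much of the ambiguity can be resolved from data the plan already collects. No summary, including a recorded reason, separates expectancy from justified trust in the seal. Severity is minor: a cheap improvement to reporting and to one form.

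**What to change.** Keep mean days between changes, the paired t test and the sample size. Then:

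1. Report leaking changes per day worn, compared within subject, for Days 0-27 and 28-55.
2. For the same periods, report mean interval at no-leak and at leaking changes within subject, the latter read with days before leakage was noted.
3. Add one reason-for-change tick-box to Appendix A in both periods (leakage, routine, skin or comfort, clinic visit, other), reported descriptively. Its main use is to separate leak-prompted changes from leaks found at removal, and to identify skin, comfort and visit changes.
4. Report Days 56-75, when longer wear is requested, separately from the comparison.

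**Cost.** One tick-box on a form already completed at each change, and a few supporting summaries. No added visits or subjects.

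**Limits.** Self-reported reasons are imperfect. Leaks per day has low power for a 20% reduction (about 13-34% at p = 10-40%, assumed inputs). It is also not fully free of habit. If every leak is found only at removal, a one-day habit shift makes it significant in 4, 4, 7 and 10% of trials at p = 10-40%, but 35% and 79% at p = 60% and 80%. If leak risk rises with days worn (Weibull shape 2), the same shift raises it by 22-27% at p = 10-40%, against the ring.

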Appendix D

1. Osto-Ring™ Evaluation Record

very easy	somewhat easy	neutral	somewhat difficult	very difficult
5	4	3	2	1

2. Satisfaction with Osto Ring™

Poor	Satisfactory	Very Good	Excellent
①	②	③	④

3. Confidence with Osto Ring™

Poor	Satisfactory	Very Good	Excellent
①	②	③	④

4. Problems with Osto Ring™

None	Few	Several	Many
①	②	③	④

Please specify any problems: _____

5. Comfort of Osto Ring™ felt

very comfortable	somewhat comfortable	neutral	somewhat uncomfortable	very uncomfortable
5	4	3	2	1

I would highly recommend the Osto Ring™ to others

Strongly Agree

Agree

Neither

Disagree

Strongly Disagree

1

2

3

4

5

6. Have you changed your pouching system in any way?

Yes

No

□

7. Is there anything else that you would like to tell us about the Osto Ring™ device?

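### Pain at application is a named component of secondary outcome 4, but neither form completed at pouch changes shows a pain item, so its with-versus-without-ring comparison cannot be made

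*Combined protocol and SAP*

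**What the plan says.** Under Secondary Outcomes, item 4 reads "Subject Ease of Use (ease of application, pain level with application, comfort, convenience of use) will be assessed using Likert scale", and the scale and source form follow as "1 = poor, 2 = satisfactory 3= very good, 4= excellent (Appendix D". Pain is listed beside comfort as a component in its own right.

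The Analysis plan opens by saying that means and frequencies will be compared with and without the ring. Its only ease-of-use summary is "Mean % of time ease of use reported as very good or excellent by subject". It lists no pain summary.

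Under Study Design, Appendix A (the Ostomy Evaluation Record) is issued at Visit One and again at Visit Two, to be completed at each change. Appendix D (the Osto Ring Evaluation Record) is issued only at Visit Two, for the ring period.

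**The concern.** The outcome points to a form that does not ask the question, and to a scale that does not suit it. A subject could tick a box from poor to excellent for pain, but nothing says whether excellent means no pain, and no category stands for its absence. The result would not be a readable pain level.

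The primary objective of this pre-market study covers safety as well as performance. The device is a stainless-steel ring, fitted by size and supplied with a belt, and the authors themselves chose pain at application as something to measure. A rating not taken at each change cannot be recovered afterwards. If the gap stays, the report will either omit a prespecified component or fill it with something other than a pain score.

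**Working it through.** The plan gives no figure on this point. Its sample size of 27 concerns wear time and plays no part here. The check is a reading of the outcome against the forms, followed by a count of the records involved.

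**Step 1. Each component of outcome 4 against the forms as shown.**

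| Component | Item found | Response scale | Poor to excellent? | Periods |
|---|---|---|---|---|
| Ease of application | Appendix D item 1 | 5 points: "very easy somewhat easy neutral somewhat difficult very difficult" | No | Ring only |
| Pain at application | None | None | No | Neither |
| Comfort | Appendix D: "5. Comfort of Osto Ring™ felt" | 5 points, comfortable to uncomfortable | No | Ring only |
| Convenience | Appendix A | 5 points, convenient to inconvenient | No | Both |

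None of the four components is collected on the stated scale. For three of them something is collected on a different scale. For pain nothing is.

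**Step 2. Where the poor-to-excellent scale is used.** In Appendix D it appears under "2. Satisfaction with Osto Ring™" and "3. Confidence with Osto Ring™" only. Neither is a component of outcome 4.

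**Step 3. The rest of the forms.**
- Appendix D also has a problems item (None to Many, with the free-text line "Please specify any problems"), a recommendation item, a question on changes to the pouching system, and an open comment. Its numbering runs from 1 to 7 without a gap, with the recommendation item unnumbered.
- Appendix A covers wear time, skin damage, odor, leakage, social freedom, convenience and satisfaction.
- Appendix B scores discolouration, erosion and tissue overgrowth.
- Appendix C is a quality-of-life form completed at visits. Its visible items (1 to 8 and 16 to 20) do not ask about pain.

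**Step 4. How many applications go unscored.** This is an illustration that rests on assumptions. Inclusion criterion 6 asks for at least two changes in seven days, so the mean interval at entry is at most 7 / 2 = 3.5 days.
- No-ring period, if the entry habit continues: 28 / 3.5 = 8 changes per subject, and 8 × 30 = 240 records.
- Ring period, if wear lengthens by the 25% used for planning: 3.5 × 1.25 = 4.375 days, 28 / 4.375 = 6.4 changes, and 6.4 × 30 = 192 records.
- Ring period, at the planning mean of 6.26 days: 28 / 6.26 = 4.47 changes, and 4.47 × 30 ≈ 134 records.

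Under each assumption the number of records with a pain score is zero.

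**The case against.** Four points on the other side deserve weight.

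**The forms are not fully visible.** Appendix C jumps from item 8 to item 16, and item 1 of Appendix D has response options but no question. A reader might infer that no form anywhere asks about pain, but the text does not establish that. What stands is narrower. Appendix C is not the form named for this outcome and is not completed at each application, and the options of Appendix D item 1 rate difficulty, not pain.

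**Pain could still surface.** A reader might infer that the study would learn nothing about pain. That goes too far. A subject could mention it under problems, in the open comment, in answer to the Day 56 question on side effects, or through an adverse event report, and the comfort item is close to it. None of these gives a graded pain level per application, and outcome 4 lists comfort separately, so comfort cannot stand in for pain.

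**The importance is limited.** Pain is one of four components of the fourth secondary outcome, and the listed ring risks do not include it. A reader might take this as a failure of the study's safety objective, or treat 240 records as a minimum in each period. The documents support neither: adverse events and skin condition are assessed separately, and criterion 6 is an entry condition that sets no floor once a device meant to lengthen wear is in use.

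**A smaller repair would remove the contradiction.** An item could be added to Appendix D, or pain deleted from outcome 4. Deletion is legitimate if the sponsor does not want the outcome. An item on Appendix D alone would give scores in the ring period only, with nothing to compare them with. It is true that Appendix A asks about the time since the last change, so an application item there needs its own wording.

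**Conclusion.** The point holds for the forms as shown. A component that the plan names, and assigns to a specific form and scale, would have no scored value in either period, so its comparison with and without the ring is unavailable, not merely imprecise. Pain may appear unscored in free text or event reports. Wear time and leakage are untouched, so this should be corrected but does not threaten the main result.

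The conclusion assumes that the unseen question for Appendix D item 1 is about ease, as its options indicate, and that the unseen items of Appendix C do not rate pain at each application, which a form completed at visits would not do. It does not depend on the record counts.

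**What to change.** 1. Add one item to Appendix A, worded for the moment of application: for example, pain when applying this pouching system, on a numeric scale anchored at no pain. Say which application is meant (the system just put on or the one just taken off), so that each score falls in the right period.
2. Adjust the instruction at the head of Appendix A, which now refers only to the time between changes.
3. Take pain out of the poor-to-excellent sentence in outcome 4 and name the Appendix A item as its source.
4. Add one line to the Analysis plan: each subject's mean pain score, compared with versus without the ring.

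Appendix A is the right place because it is completed in both periods and the plan already reports its items individually. The cost is a few seconds per change for the subject and a small edit to the form. If the sponsor does not want this outcome, it should delete pain from outcome 4.

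### The study is titled randomized and promises adjustment for order of ring use, but every subject gets the ring second, so the adjustment cannot be done and ring cannot be separated from period

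*Combined protocol and SAP*

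**What the plan says.** The title reads "A randomized controlled trial to assess the performance and safety of a novel Ostomy Ring".

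Under Research Design, the 30 subjects are described as "acting as their own controls" and first use their usual pouching system without the ring for 28 days. Then: "On Day 29 subjects will be switched to the Osto-Ring regimen until day 56". Visits One to Three under Study Design repeat this one sequence for everyone. At Visit Two, "They will be fitted for the proper Osto-Ring size and given a belt". From Day 56 subjects choose whether to go on with the ring, and no return to the ring-free condition is planned for comparison.

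The Analysis plan says that all means and frequencies, with and without the ring, "will be controlled for the order in which a subject used the Osto Ring". It also says "We will compare the baseline characteristics of the two groups", using a paired t test for continuous variables and the Fisher exact test for categorical ones.

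**The concern.** The title and the Analysis plan describe a study in which order varies between subjects. The schedule describes one in which it does not. If the schedule is what will be done, two statements in the plan fail: allocation is not randomized, and the order adjustment cannot be carried out. The order sentence covers every compared mean and frequency, including wear time and leakage, which are primary outcomes.

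A reader of the results would believe that change over time had been handled by randomization and again by adjustment, when neither had happened. Any difference between the first and second 28 days that has nothing to do with the ring would be credited to the ring.

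There is a smaller, separate question about what is being tested. A belt is handed out at ring fitting. The documents do not say whether it is part of the device, whether it must be worn, or whether some subjects already use one. Until they do, the estimate is for ring plus belt.

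**Working it through.** **The plan's own figure.** Inputs from the sample-size paragraph: mean wear time 5.01 days, SD 2.25, target 6.26 days, paired t test, alpha 0.05 (two-sided assumed, since sidedness is not stated), power 0.80.

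- Effect size: (6.26 − 5.01) / 2.25 = 1.25 / 2.25 = 0.556, given as 0.56.
- Two-sided paired t test at 0.56: n = 27.01, with power 0.7998 at 27. The stated 27 reproduces, and power at the planned 30 is 0.842.

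The sample size is for an unadjusted paired test and is not affected by this point.

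**Can order or period be adjusted for?** Take one row per subject per period and count the independent columns of the design matrix.

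| Model | n | Columns | Rank, schedule as written | Rank, two orders |
|---|---|---|---|---|
| Subject + ring + period | 27 | 29 | 28 | 29 |
| Subject + ring + period | 30 | 32 | 31 | 32 |
| Intercept + ring + order | 27 or 30 | 3 | 2 | 3 |

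Under the schedule the ring column equals the period column (correlation 1.0), and order takes a single value. With subject terms in the model, an order term adds no rank in either design, because order is fixed within a subject. Period is the term that a second sequence makes estimable.

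**What the paired test then estimates.** Mean of (second period − first period) = ring-regimen effect + period effect. One equation cannot separate the two.

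**How much a shift would matter (illustration; the shifts are assumed).** With no ring effect and a true shift s, the two-sided rejection probability is P(|T| > t(0.975, n−1)), where T is noncentral t with n−1 df and noncentrality s√n / SD. Two SDs of the paired differences are used:

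- 2.25 days. This is the protocol's figure, which it calls a pooled SD; using it for differences is an assumption.
- 1.57 days, from 3.5 × 2.25 / 5.01. This assumes a constant coefficient of variation and a mean of 3.5 days, the longest mean that fits the entry rule "Change their pouching system at least two times in seven days" (7 / 2 = 3.5).

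| Assumed shift | Share of 1.25-day target | n = 27, SD 2.25 (SD 1.57) | n = 30, SD 2.25 (SD 1.57) |
|---|---|---|---|
| 0.25 day | 20% | 9% (12.5%) | 9% (13%) |
| 0.5 day | 40% | 20% (36%) | 22% (39%) |
| 1.0 day | 80% | 60% (89%) | 65% (92%) |

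The nominal rate is 5%.

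**Power if order were randomized.** With treatment and period terms the residual df fall from n−1 to n−2. At 1.25 days and SD 2.25, power is 0.836 at 30 subjects and 0.792 at 27, against 0.837 and 0.794 for the unadjusted paired test. Adjusting for period costs almost no power.

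**The case against.** A fixed-sequence before-after study is a legitimate design, and the Research Design states the sequence openly. The planned paired t test can be run. Subjects have had a stoma for at least 6 months and the same system for at least 8 weeks, and the same change record and photographs are required in both periods. All of this limits learning and diary effects. It stands, and it is why the minimum fix does not ask for a redesign. It does not make the title true or the order adjustment possible.

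The strongest technical objection is that two rows per subject understate the data. A record is completed at every pouch change, and two changes a week give about 8 records per 28 days. With 8 records per period for 30 subjects, a model with subject, ring and a linear day trend has full rank, 32 of 32. A gradual drift could therefore be examined. The price is a linearity assumption and, with a ring–day correlation of 0.87, about 4 times the variance for the ring term (1 / (1 − 0.87²) ≈ 4.1). A step change at the switch, or an expectation effect in an open-label study, still cannot be separated from the ring. This supports a sensitivity analysis, not the order adjustment.

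The baseline comparison could be read as comparing skin score and quality of life at Visit One with Visit Two. That would be informative about drift in the control period, but it does not compare two groups, and fixed characteristics would be identical by construction.

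The shift sizes have no source in the documents. That is correct: the table shows sensitivity and is not evidence that a drift exists. The conclusion rests on the ranks.

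**Conclusion.** The concern holds and must be fixed. As scheduled, the study is not randomized, order of ring use is constant, and ring is completely aliased with an arbitrary period effect (rank 31 of 32 at 30 subjects, 28 of 29 at 27). This follows from the schedule alone and needs no assumed figure.

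The size of any resulting bias is unknown. If a shift of 0.25 to 1.0 day existed with no ring effect, the false-positive rate at 30 pairs would be 9% to 65% with an SD of differences of 2.25, or 13% to 92% with 1.57. The documents neither show such a shift nor allow a step change to be excluded. The result cannot be reported as a randomized or order-adjusted comparison.

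**What to change.** **Minimum.** Reconcile the title and Analysis plan with the schedule:

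1. Remove *randomized* from the title.
2. Delete the order adjustment and the two-group baseline comparison, and describe baseline once for the single group. If a Visit One to Visit Two comparison of skin score and quality of life was intended, specify it as a check on change during the ring-free period.
3. Describe a single-group, fixed-sequence before-after study of the ring regimen, and state whether the belt is part of that regimen.
4. Report the paired difference with a 95% CI, and state that it cannot be separated from a period effect. A linear-trend analysis of the per-change records can be added as a sensitivity analysis, with its limits stated.

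This costs text edits to the title, Research Design and Analysis plan. No extra subjects, visits or data are needed.

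**Only if the sponsor wants to keep the randomized claim.** Randomize order 1:1 and analyse the within-subject data with treatment and period terms (power 0.836 at the planned 30). This costs more. It needs an allocation list and ring fitting at Visit One for half the subjects. Visits Three and Four must also be rewritten, because they assume the ring has just been worn, including the request that "subjects will be asked to extend the wear of their devices by 1-4 days". There is no washout, so carry-over through skin condition or changing habits would have to be accepted or addressed, and open-label expectation effects would remain.
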